Ocular protection: In addition to providing the ocular surface with moist, ocular protection in the forms of drops has proved advantageous. Sodium hyaluronate and disaccharides have been included in eye drops with the aim of increasing ocular protection. Sodium hyaluronate containing solutions have been demonstrated to result in improvement in dry eye in patients compared to other lubricant solutions in several studies.^{13,14} Naturally occurring disaccharides, which are a major component in Thealoz, are used with the purpose of protecting the cells of the cornea and conjunctiva as well as to give resistance to dryness. Thealoz has proved successful in clinical studies.^{15,16}

Study Description

Aims: To compare the effects of THERA°PEARL Eye Mask with the use of Blephasteam®.

Study Design

All the studies will be conducted based on written consent of the patients. Moreover, they will be performed in accordance with the tenets of the Helsinki Declaration and after approval from the Regional Ethics Committee as well as. If the patients encounter any problems during the study, they will be examined, irrespective of the planned follow-ups. The patients are free to quit the study at any time for any reason.

To answer our aim, we have, in brief, chosen the following study design:

1) THERA°PEARL Eye Mask versus treatment with Blephasteam®. In both groups, 60 patients with MGD are enrolled. We aim to make the two groups comparable as to the severity of the disease, age, and gender. The patients will be examined before the treatment and after 3 months, and 6 months. Treatment for both groups will be according to the manufacturer. All the analyses mentioned in the section *analyses* are planned to be included at every examination. Inclusion criteria: Meibomian gland dysfunction and candidate for eyelid heat therapy. Diagnosis of at least mild severity will be based upon recommendation by the diagnostic subcommittee of the International Workshop on Meibomian Gland Dysfunction, as seen in Table 1.

Ocular Surface Disease Index (OSDI)	>12
Quality or expressibility score	≤20 years old: >1 >20 years old: ≥1
Non-invasive tear film break-up time (NITBUT)	<10 s in at least one eye
Schirmer-1 test	>5 mm after 5 min in at least one eye

Exclusion criteria: Glaucoma, ocular allergy, autoimmune disease, contact lens-wear during study, current punctal plugging, pregnant/lactating, candidate for topical anti-inflammatory therapy, or cicatricial MGD.

Analyses

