Keratograph 5M. Keratograph 5M (Oculus, Germany) technology will be used to enable meibography, which is a novel *in vivo* technique that provides photographic documentation of the meibomian gland, including the ducts and acini, under specialized illumination. *In vivo* confocal microscopy has the advantage of very high resolution, but at the expense of the overview. Both detailed analyses of selected glands and an overview of the general health of all the glands in the eyelids are important to be able to decide upon the best treatment strategies.

Integrative approach. The Dry Eye WorkShop (DEWS) severity scale³⁰ will be used as it integrates the values derived from the following analyses in one single score: tear osmolarity, Schirmer tests, TBUT, corneal staining, meibomian score, conjunctival staining, and OSDI.

Data Management and Statistical Analysis Plan

All data will be stored in a special electronic medical record system built for management of dry eye disease. The extraction of the patient data from the system database will be carried out according to guidelines by the Regional Ethical Committee and the Norwegian Data Protection Agency. The dataset will be de-identified prior to any statistical analyses.

All data will be checked for normality to determine the appropriate parametric or non-parametric test. To test for differences among groups, relevant Chi square test, one-way analysis of variance (ANOVA) and Kruskal–Wallis equality- of-populations rank test will be used. Where there is difference among groups, relevant Student's t test or Wilcoxon rank sum test will be performed. Chi square test will be used to evaluate the differences in the primary and secondary outcomes between groups. Logistic regression will be used to adjust for baseline differences. Statistically significant difference is based on 0.05 level of significance. All analyses will be performed with SPSS software, version 24 (IBM Corp., NY, USA).

Missing data will be handled with last observation carried forward.

Zero-hypotheses: Blephasteam® (Spectrum Thea Pharmaceuticals LTD, Macclesfield, UK) and THERA°PEARL Eye Mask (Bausch & Lomb Inc., New York, USA) differ by a clinically relevant amount. Type I error rate of 0.05 and power (type II error rate) 0.20. There are many parameters that will be measured in the study, the primary being tear film break-up time (TFBUT).

Originality and Scientific/Clinical Value

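### Covariates for the device comparison are not fixed in advance; tying adjustment to observed baseline differences could leave out the balancing factors and baseline TFBUT, mainly at a cost in power

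*Combined protocol and SAP*

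**What the plan says.** The section *Data Management and Statistical Analysis Plan* compares primary and secondary outcomes between groups with a chi-square test, and then adds one sentence on adjustment: "Logistic regression will be used to adjust for baseline differences". It lists no covariates and does not say what counts as a difference. Elsewhere the section gives a general threshold ("Statistically significant difference is based on 0.05 level of significance") and describes follow-up tests that are run where groups are found to differ.

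*Study Design* says of the allocation: "We aim to make the two groups comparable as to the severity of the disease, age, and gender". The text does not say how this is to be done (stratification, matching, minimisation or otherwise), and it does not describe this study's own allocation as random.

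The primary outcome is TFBUT. The section *Analyses* describes fluorescein break-up time as the mean of three stopwatch readings, that is, a time in seconds. No cut-off is given that would turn it into a yes/no outcome for logistic regression.

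**The concern.** The two sections pull against each other. The design tries to remove differences in severity, age and gender, while the analysis adjusts for differences. The better the design succeeds, the less reason the analysis has to include the factors on which it was built. Baseline TFBUT, usually the obvious covariate for follow-up TFBUT, has no guaranteed place either.

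Three things are at stake, each under a different condition:

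- If allocation is restricted on the factors and the analysis ignores them, the standard error is overstated and the test is conservative.
- If allocation is simply random, power is lost.
- If allocation is not random, imbalances that go unnoticed bias the comparison.

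Overstated standard errors matter more than usual here. The stated null hypothesis is that the devices "differ by a clinically relevant amount", which points to an equivalence aim, and wide intervals make equivalence harder to show. In every case, the choice of model stays open until the baseline data have been seen.

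**Working it through.** **The plan's own figure.** The plan states "In both groups, 60 patients with MGD are enrolled" and "Type I error rate of 0.05 and power (type II error rate) 0.20", but gives no difference and no SD, so 60 per group cannot be reproduced. Reading the 0.20 as the type II error (power 0.80) and assuming a two-sided test, the standardised difference that fits is 0.511: n = 2 × (1.960 + 0.842)² / 0.511² = 15.70 / 0.261 ≈ 60. An effect of 0.5115 SD is used below as a working value.

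**Inputs.** From the documents: 60 per group and alpha 0.05. Assumed, because the documents are silent: two-sided testing of a difference; outcome SD of 1; share of outcome variance explained by the covariates, R² = 0.10, 0.25 or 0.50; a p<0.05 screen wherever one is simulated. Simulated values are from 4,000 runs per setting unless stated otherwise.

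**Step 1: unadjusted analysis.** Reported SE = √(2/60) = 0.1826 SD. With 118 degrees of freedom, a difference is significant when it exceeds 1.980 × 0.1826 = 0.3615 SD.

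**Step 2: balancing factors fixed by design but left out of the model.** With exact balance, the true SE is 0.1826 × √(1 − R²), so the reported SE is too large by the factor 1/√(1 − R²).

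| | R² 0.10 | R² 0.25 | R² 0.50 |
|---|---|---|---|
| True SE (SD units) | 0.173 | 0.158 | 0.129 |
| Reported SE / true SE | 1.05 | 1.15 | 1.41 |
| Type I error, factors left out (simulated) | 0.039 | 0.026 | 0.008 |
| Power at 0.5115 SD, factors left out (simulated) | 0.81 | 0.83 | 0.87 |
| Power at 0.5115 SD, fixed adjustment (simulated) | 0.84 | 0.90 | 0.98 |

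With fixed adjustment the type I error is about 0.05 throughout. As a check on the left-out power: Φ((0.5115 − 0.3615) / true SE) = Φ(0.87), Φ(0.95), Φ(1.16) = 0.81, 0.83, 0.88, in agreement with the simulation.

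**Step 3: simple randomisation.** Take a covariate-outcome correlation of 0.5 (R² = 0.25). Mean bias is about zero whether or not the covariate is used. Power at about 0.51 SD is 0.79 to 0.80 if the covariate enters only when it differs at p<0.05, and 0.89 if it always enters. The screened analysis is slightly conservative, with type I error of 0.036 to 0.048 across the three R² values.

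**Step 4: non-random allocation.** Assume a true difference of 0.3 SD between the arms on a covariate correlated 0.5 with the outcome.

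- Chance that a p<0.05 screen flags it: 0.3 / 0.1826 = 1.64, and Φ(1.64 − 1.98) ≈ 0.37. It is missed about 63% of the time.
- Never adjusting: bias 0.3 × 0.5 = 0.15 SD, which is 0.15 / 0.1826 = 0.82 SE, with a false-positive rate of about 0.13.
- Adjusting when flagged (simulated, up to 20,000 runs): mean bias about 0.06 SD and type I error about 0.06. Among the trials where the screen misses, bias is about 0.09 to 0.10 SD and type I error about 0.065. These are lower than for never adjusting because trials that pass the screen have smaller observed imbalances.
- Always adjusting: bias about zero and type I error about 0.05.

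Over imbalances of 0.2 to 0.3 SD and R² from 0.10 to 0.50, adjusting when flagged leaves a mean bias of 0.04 to 0.08 SD and a type I error of 0.052 to 0.065.

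**The case against.** The strongest reply is that the adjustment sentence contains no significance test, threshold or selection rule, and could be read as adjustment for baseline characteristics in general. That is fair. A reader might infer that severity, age and gender will certainly be dropped by a p<0.05 screen. The documents permit this but do not say it, so the supportable statement is that these factors could be left out.

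Second, a reader might infer that the error bars are wrong. That needs allocation actually restricted on these factors, and *Study Design* states only an aim. With loose or chance balance the conservatism shrinks or disappears, and at R² = 0.10 it is small even under exact balance.

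Third, a reader might infer a bias of 0.15 SD and a false-positive rate of 0.13. Those figures belong to an analysis that never adjusts, in a trial with a systematic difference between the arms. They do not describe adjusting when a difference is seen, and under randomisation the average bias is zero. The available text does not name the allocation method, and that silence does not establish that allocation was non-random.

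What remains is that no covariate is fixed, the main test is unadjusted, and nothing commits the analysis to information that the trial already collects or intends to balance on.

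**Conclusion.** The point holds as a weakness in the covariate rule. Its main expected cost is lost power and, under restricted allocation, overstated standard errors. It is not a demonstrated bias.

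- **Restricted allocation:** the standard error is 5% to 41% too wide and the power loss at 0.51 SD runs from 0.03 to 0.11, depending on how much variance the factors explain.
- **Simple randomisation:** a loss of about 0.10 in power at a correlation of 0.5.
- **Non-random allocation:** mean bias of about 0.06 SD and type I error of about 0.06 for a 0.3 SD imbalance, if a p<0.05 screen is used.

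The R² values, the correlation, the imbalance, the screen and the 0.51 SD effect are all assumptions; the documents give none of them. The error rates are for a two-sided test of a difference. Fixed adjustment gave close to nominal error and no bias in every setting examined, though it can only deal with the covariates that are in the model.

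**What to change.** State the allocation method, and replace the adjustment sentence with wording such as:

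> The device comparison of TFBUT in seconds uses a linear model (ANCOVA) adjusted for baseline TFBUT, baseline severity (the measure used to form the groups), age and gender. These covariates are fixed before data are seen and kept whatever the baseline table shows. Baseline significance tests are not used to choose covariates, and any further adjustment is a sensitivity analysis.

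For the other outcomes, use the corresponding baseline value and a model suited to the scale. Logistic regression should be kept for outcomes that are binary by a stated definition.

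The cost is SAP wording. Baseline TFBUT and measures of severity are already collected, and age and gender are factors the design already intends to balance. The model uses about four degrees of freedom out of 118 (120 patients minus two group means).

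### Last observation carried forward is the only missing-data rule, and with just two follow-up visits it can bias the comparison of the two devices

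*Combined protocol and SAP*

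**What the plan says.** The section Data Management and Statistical Analysis Plan has one sentence on the subject: "Missing data will be handled with last observation carried forward". It does not say which values may be carried, what is assumed about why data are missing, or how sensitive the result is to that assumption. No expected loss is given.

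The same section names TFBUT as primary and says "Chi square test will be used to evaluate the differences in the primary and secondary outcomes between groups", without defining a response. It adds "Logistic regression will be used to adjust for baseline differences". The null hypothesis is worded as the devices being such that they "differ by a clinically relevant amount"; the amount is not stated.

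Study Design sets the visits: "The patients will be examined before the treatment and after 3 months, and 6 months". It also says "The patients are free to quit the study at any time for any reason", and provides for extra examinations: "If the patients encounter any problems during the study, they will be examined, irrespective of the planned follow-ups". It does not say whether values from those examinations count as observations.

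**The concern.** With two follow-up visits, the value carried to month 6 can only be the pre-treatment value or the month-3 value, unless an unscheduled examination supplies another. A pre-treatment value is not a plausible 6-month result for a patient whose eyes would have improved. If response means a gain from baseline, a patient with a carried-forward baseline has change zero and counts as a non-responder.

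Two harms follow, depending on how the hypothesis is read. Under the null as worded, anything that shrinks a real difference favours a finding of similarity, so the usual defence that carrying forward is conservative does not apply. Under the difference tests that the plan names, a higher loss with one device can make two equal devices look different. The devices are used differently (warming goggles and a microwave-heated mask), so equal loss cannot be taken for granted.

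**Working it through.** **Inputs from the documents.** 60 patients per group (Study Design: "In both groups, 60 patients with MGD are enrolled"); visits before treatment, at 3 and at 6 months; type I error 0.05 and type II error 0.20.

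**Assumed, because the documents give no figure.** Loss *p*; share *e* of losses before month 3; mean gains at months 3 and 6; correlation 0.6 between visits; comparable groups at baseline. All effects are in SD units.

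**The plan's own figure.** The 60 per group cannot be reproduced without an effect, SD or margin. Solved backwards:
- Difference test, two-sided 0.05, 80% power: (1.960 + 0.842) × √(2/60) = 0.51 SD.
- Equivalence test, one-sided 0.05, true difference zero: (1.645 + 1.282) × √(2/60) = 0.53 SD.

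The illustrations use 0.54 SD, close to both.

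**Step 1, equal loss unrelated to outcome.** With true device differences d3 and d6, the expected carried-forward difference is d6 − p[e·d6 + (1 − e)(d6 − d3)]. At p = 0.20 and d6 = 0.54:
- Half early, stable (d3 = 0.54): 0.54 − 0.20 × 0.27 = 0.486.
- Half early, growing (d3 = 0.27): 0.54 − 0.20 × (0.27 + 0.135) = 0.459.
- All late, stable: 0.54, no bias.
- All late, waning (d3 = 0.81): 0.54 + 0.20 × 0.27 = 0.594.

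Suppose the margin is also 0.54 SD and the analysis is a baseline-adjusted linear one with a 90% interval, which the plan does not itself name. Simulated false equivalence is then 9 to 14% in the half-early cases, 5% for stable late loss and 2% for waning. A likelihood-based mixed model stays at about 5%. At 5% loss, half early, carrying forward gives 6 to 7%.

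**Step 2, equal devices, unequal loss unrelated to outcome.** Each group's expected carried-forward gain is g6 − p[e·g6 + (1 − e)(g6 − g3)]. With g6 = 1 and half the losses early:
- Gain complete by month 3 (g3 = 1): 1 − 0.5p. At 5% and 25% loss this is 0.975 and 0.875, a false difference of 0.10.
- Gain half complete (g3 = 0.5): 1 − 0.75p. This is 0.9625 and 0.8125, a false difference of 0.15.

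Simulated rejection at a nominal 5%, for the two cases:

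| Analysis | g3 = 1 | g3 = 0.5 |
|---|---|---|
| Baseline-adjusted linear | 10.3% | 16.9% |
| t test | 8.5% | 12.6% |
| Chi-square, response = gain of 1 SD or more | 9.0% | 13.0% |
| Chi-square, response = gain of 0.5 SD or more | 13.3% | 18.4% |
| Mixed model | 5% | 5% |

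At 10% versus 20% loss, the same formulas give 0.05 and 0.075 SD, with linear rejection of 6.4% and 7.6%. If neither device gives any gain, there is no bias.

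**Step 3, loss of poor responders.** Here loss depends on the unseen month-6 change (logistic slope 1.48 per SD).
- Equal devices, 25% v 15% lost: mixed-model bias 0.06 to 0.07 SD, rejection 7 to 8%. Carrying forward: at most 0.04 SD, 5 to 6%.
- Equal devices, 25% v 5% lost: mixed model 0.12 to 0.14 SD, rejection 12 to 15%. Carrying forward: at most 0.09 SD, 5 to 9%.
- True difference 0.54 SD, equal 20% loss: mixed model 0.54 SD; carrying forward 0.46 to 0.54 SD, nearer the truth in 0 of 12 settings.
- True difference 0.54 SD, 25% v 15% lost: carrying forward nearer in 8 of 12 settings when the worse device loses more, and in 7 of 12 when the better one does. Over these and the equal-loss settings, the largest error was 0.14 SD for carrying forward and 0.07 SD for the mixed model.

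**The case against.** The strongest objection concerns the remedy. In the harm feared most, equal devices made to look different by unequal loss of poor responders, the mixed model was further from the truth than carrying forward in all 12 settings examined. With a true difference and unequal loss, carrying forward was nearer in 15 of 24. This stands. It means that a mixed model alone is not enough. It does not rescue carrying forward as the sole method: there it did better because errors offset each other, and it fails under random unequal loss, where the mixed model does not. Delta adjustment recovers the truth only with the right deltas, which nobody will know, so it must be reported as a range.

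A second objection is size. For the chi-square test that the plan names (assumed response: gain of 1 SD or more), power at 20% equal loss, half early, is 58 to 64% with carrying forward and 63 to 64% on observed data if the comparator gains 1 SD. If it gains nothing, the figures are 52 to 59% and 54 to 55%. So the effect on power may be small, nil or even favourable. Freedom to withdraw is not evidence that withdrawal will depend on outcome. Both points stand.

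A reader might also infer that every patient lost before month 3 is counted as a non-responder. The documents do not support that: unscheduled examinations may supply a post-treatment value, the plan does not say that baselines are carried forward, and response is undefined. Nor does carrying forward always shrink the difference. With 20% early loss in each group and a true 0.54 SD, it gave 0.71 SD when the better device lost poor responders and the other lost good ones, and 0.16 SD in the reverse case.

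**Conclusion.** The concern holds in a limited form. The sole missing-data rule can give a biased device comparison even when loss is unrelated to outcome, and nothing in the text available for review would reveal it. Under the assumptions shown, 5% versus 25% random loss gives 0.10 to 0.15 SD of bias and about 10 to 17% false rejection in the linear analysis. Equal 20% loss, half early, shrinks 0.54 SD to about 0.46 to 0.49 SD. The bias is small at 5% equal loss and nil for late loss with a stable effect.

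Every size is illustrative. The documents give no loss rate, SD, trajectory, margin or response definition, so a reader should not infer that this trial's result will be wrong by any stated amount, or that a mixed model is better in all circumstances. The change should be made. Confidence is medium: the rule is plain in the text, but its effect here cannot be sized.

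**What to change.** Before outcome data are seen, replace last observation carried forward as the main method for TFBUT with an analysis that is valid when loss depends on observed data. Either route would do:

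- a likelihood-based mixed model on observed month-3 and month-6 values, with device, visit, device-by-visit, baseline TFBUT by visit, and unstructured covariance; or
- if the planned chi-square and logistic analyses are kept, multiple imputation of TFBUT from device, baseline and month 3 before response is classified.

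The choice of primary test and time point is a separate matter.

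The following belong to the same change:

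- A required delta-adjusted multiple imputation that includes patients lost before month 3, who contribute no outcome to the mixed model (6 of 60 per group at 20% loss, half early). Vary delta separately by group. The estimate moves by pA·δA − pB·δB: at 20% loss, a delta of 0.5 SD in one group moves it by 0.20 × 0.5 = 0.10 SD, and the same delta in both groups with equal loss does not move it. State beforehand what would count as a changed conclusion; under the null as worded this needs the missing margin.
- A statement on whether values from unscheduled examinations count.
- Losses and reasons reported by group.
- Last observation carried forward kept, at most, as a labelled sensitivity analysis.

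The cost is one paragraph and a little more analysis work, with no added patients or visits. At 20% loss, half early, the standard error goes from 0.142 SD (comparator gains nothing) or 0.158 to 0.160 SD (gains 1 SD) to 0.163 SD. In the case kindest to carrying forward (all losses late, stable effect) it goes from 0.146 to 0.162 SD, and power for 0.54 SD falls from about 95% to 91%.

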countries. For example, at the Department of Ophthalmology, Harvard Medical School, DED is a highly prioritized field with several research groups working on improved treatment modalities. Research on DED holds the prospect to significantly improve quality of life for hundreds of thousand people in Norway. In addition, research on DED is critical to maximize the clinical outcome of some of the most severe forms of visual impairment that necessitate ocular surface stem cell treatment and/or corneal transplantations. Without an adequate tear film, these transplants will inevitably fail. Therefore, research on DED has the potential to help patients with the most severe visual impairments, either directly (in the event of keratinizing DED) or indirectly by enhancing the clinical results of other surgical procedures. In the light of DED being both a widespread disease and having huge implications for maximizing outcome of several diseases and treatments in ophthalmology, several members of our research group has taken measures to contribute to lessening DED in the Norwegian population. One example is the establishment of the Norwegian Dry Eye Clinic, which is the first specialized clinic for DED in Scandinavia.

Treatment Options for Meibomian Gland Dysfunction

There are several treatment options for MGD, but yet no consensus on the best approach. Lid scrubs using for example mild shampoo, eyelid massage and warm compresses of the eyelids, belong to the basic therapy. In addition, a large number of medications have been suggested over the past years for more severe forms of MGD. Comparative studies between possible treatment strategies are warranted to be able to conclude on the best available options.

Basic Therapy

Good eyelid hygiene, warming and massage are considered an effective mainstream therapy for MGD and blepharitis, in spite of the lack of standardization of the technique as well as the uncertainty about patient compliance. Studies comparing different methods of mainstream 4 therapy, such as eyelid warming, would allow evidence-based recommendations. The diversity of recommendations for such basic treatment is exemplified by the advice given in two leading textbooks of ophthalmology:

- “Warm wet face cloth for 5 minutes once or twice a day, and massage upper and lower lid (Moorfields Manual)”
- “Warm compresses for 15 minutes four times per day, and clean with wet cotton bud and mild (baby) shampoo (Will’s Eye Manual)”.

Recent advances

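### The stated null hypothesis is an equivalence null with no margin, but every planned test has a no-difference null, so no planned result can reject it

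*Combined protocol and SAP*

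**What the plan says.** The Data Management and Statistical Analysis Plan section gives one hypothesis, labelled as the null: Blephasteam and "THERA°PEARL Eye Mask (Bausch & Lomb Inc., New York, USA) differ by a clinically relevant amount". The error rates follow directly: "Type I error rate of 0.05 and power (type II error rate) 0.20". Tear film break-up time (TFBUT) is named as primary.

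The tests come earlier in the same section. Chi square, one-way ANOVA and Kruskal–Wallis are to look for differences among groups. Student's t or the Wilcoxon rank sum follows where a difference is found. For the outcomes themselves, "Chi square test will be used to evaluate the differences in the primary and secondary outcomes between groups". Logistic regression adjusts for baseline differences. The only decision rule is "Statistically significant difference is based on 0.05 level of significance".

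Elsewhere, the aim under Study Description is neutral: "To compare the effects of THERA°PEARL Eye Mask with the use of Blephasteam". The background on treatment options says "Comparative studies between possible treatment strategies are warranted to be able to conclude on the best available options". The Study Design section enrols 60 patients per group and gives the visits: "The patients will be examined before the treatment and after 3 months, and 6 months".

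The text supplied contains no margin, no value for the clinically relevant amount, no equivalence or non-inferiority procedure and no confidence-interval rule.

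**The concern.** A null asserting that two treatments differ by a relevant amount is rejected only by showing that the difference lies inside a margin. The planned tests cannot do this. Their null is that the groups do not differ, so the hypothesis and the tests face in opposite directions.

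The plan's error rates are at stake. The 0.05 is meant to be the chance of wrongly rejecting the null, but no planned test addresses the null that is written. The 0.20 is the chance of missing a real difference under one reading and of failing to show equivalence under the other. The plan does not say that a non-significant result will be read as equivalence, but a null worded this way leaves that misreading open.

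**Working it through.** **1. Null against tests.** Write δ for the true difference in TFBUT and Δ for the clinically relevant amount.

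| | Null | Rejected by |
|---|---|---|
| Stated hypothesis | \|δ\| ≥ Δ | evidence that −Δ < δ < Δ |
| Chi square, ANOVA, Kruskal–Wallis, t, Wilcoxon rank sum | no difference between groups | evidence of a difference |

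- p < 0.05 rejects no difference. It does not reject \|δ\| ≥ Δ.
- p ≥ 0.05 rejects nothing. It shows neither a difference nor equivalence.
- Δ has no number, unit or scale, so a confidence interval cannot be compared with it either.

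This step uses no assumed figures and establishes the contradiction by itself.

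**2. The plan's own figure.** The 60 per group cannot be reproduced, because no SD, target difference or margin is given. The calculations below work back from 60.

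**3. Inputs.** From the documents: n = 60 per arm, α = 0.05, and 0.20 read as the type II error (80% power). Assumed: complete data, a normal outcome, differences in SD units, a two-sided difference test, and 5% on each side for the equivalence test. The standard error is √(2/60) = 0.183 SD, with 118 degrees of freedom. These figures describe a t-type analysis of TFBUT as a continuous outcome. They do not describe the chi-square test that the plan names for the outcomes.

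**4. Difference test.** Power comes from the noncentral t distribution with noncentrality d·√(60/2) and critical value 1.980.

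| True difference (SD) | Noncentrality | P(non-significant) | n per arm for 80% power |
|---|---|---|---|
| 0.5 | 2.74 | 22% | 64 |
| 0.4 | 2.19 | 42% | 100 |
| 0.3 | 1.64 | 63% | 176 |

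Power reaches 80% at d = 0.516 SD. If Δ were one of these values and non-significance were taken as rejecting the stated null, the third column would be the false-rejection rate with the true difference exactly at Δ, against the stated 5%.

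**5. Equivalence test.** The two one-sided tests (TOST) declare equivalence if the 90% confidence interval lies wholly within ±Δ. The half-width with sample SD 1 is 1.658 × 0.183 = 0.303 SD. Power is integrated over the sampling distribution of the SD, with true difference 0.

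| Margin (SD) | Power, 60 per arm | Power, 54 per arm (assumed 10% loss) | n per arm for 80% power |
|---|---|---|---|
| 0.5 | 72% | 65% | 70 |
| 0.4 | 41% | 33% | 108 |
| 0.3 | 3% | 1% | 191 |

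The margin giving 80% power is 0.537 SD at 60 per arm and 0.567 SD at 54. When the true difference equals the margin, TOST declares equivalence with probability at most 0.05, which is the control that the stated null calls for.

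A true difference of zero is the most favourable case. At a margin of 0.537 SD, power falls to 73% if the true difference is 0.1 SD and to 57% if it is 0.2 SD.

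**The case against.** The best reply is that this is a drafting slip, with the alternative written where the null belongs. The aim is neutral, the background looks for the best option, the analysis section speaks of differences throughout, and equivalence is never mentioned. The same paragraph has another evident slip, since it labels 0.20 as both power and type II error. On this reading, correcting the null changes no patient or visit, and the harm described is conditional.

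Much of this stands. A slip is at least as plausible as an equivalence aim. But the documents do not prove it, and a slip in the only stated hypothesis still has to be corrected. The clinically relevant amount is also left without a value under either reading.

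The numerical illustration has limits too. It rests wholly on assumed SD-unit differences and does not model the chi-square test. It therefore shows neither that 60 per arm is adequate nor that it is inadequate. The contradiction does not depend on it.

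Finally, part of the document that follows the statistical section was not available, so the absence of a margin can be asserted only for the text supplied.

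**Conclusion.** The concern holds and must be fixed. As written, the null and the tests contradict each other, and no result of the planned analysis can reject the stated null. Neither error rate belongs to a defined hypothesis.

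The practical size depends on figures that the plan does not give. Under the assumptions above, 60 per arm has 80% power for a difference of about 0.52 SD or more, or for showing equivalence within about 0.54 SD if the true difference is zero. A non-significant result would be weak evidence against differences of 0.3 to 0.5 SD. The unnamed primary time point is a separate gap and adds no weight to this finding.

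**What to change.** Before outcome data are seen, state the objective, then align the null and the primary test.

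**(a) If a difference is sought**, as the aim and the tests suggest:
- Rewrite the null as no difference in TFBUT.
- Make the t test or the Wilcoxon rank sum the primary test. Both are listed, but only as follow-on tests, so the sentence assigning chi square to the outcomes must change.
- State the target difference in seconds and report the estimated difference with its 95% confidence interval.
- State that a non-significant result will not be reported as equivalence.

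Cost: SAP wording and a stated target difference; aligning null and test needs no extra patients. The trial then cannot claim equivalence.

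**(b) If equivalence is sought**:
- Keep the null and prespecify a clinically justified margin in seconds.
- Declare equivalence only if the 90% confidence interval for the TFBUT difference lies wholly within plus or minus that margin.
- Restate power for that margin. The margin must not be chosen to fit the sample size.

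Cost: SAP wording, a justified margin and possibly more patients. With no dropout and a true difference of zero, 60 per arm gives 80% power only for margins of about 0.54 SD or wider. Margins of 0.5, 0.4 and 0.3 SD need about 70, 108 and 191 per arm before dropout.

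In both cases, name 3 or 6 months as the primary time point. Neither option adds visits.
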